5B) Setting & Sample. The target sample will be recruited in **5 sites**. We will continue the working relationships we built while conducting our R21 RCT with Spectrum Health, McLaren, and Sparrow Health. We will add Munson Healthcare and Nebraska Medicine Campus. Results from our R21 RCT show very large effect sizes between the exercise and usual care groups that are not expected to hold in this proposed study as we have additional sites with more diverse populations and two new study arms (ACG and WCG). Our sample size assessment for primary Aim 1 uses the expected CRF severity scores by age group shown in **Table 1 (below)** with CRF estimates from our R21 RCT for comparison. An exemplar multiple regression model was run with age distribution approximating the NSCLC population with 33% < 65 yrs and 67% ≥ 65 yrs, model error standard deviation (SD) = 2.0. Comparable R21 results suggest a SD between 0.7 and 2.6 in these two age groups. With overall significance level at 5%, we computed the total sample size N to ensure at least 80% power in 4 pre-specified comparisons between IIG and ACG for ages <65 and ≥ 65. With N = 180 (60/group, 20 <65 yrs and 40 ≥ 65 yrs) power to detect the expected CRF is shown in **Table 2 (below)** with the minimum sample size for each comparison. Based on our R21 RCT and previous cancer work,¹¹⁵ we will over-recruit to account for a conservative attrition rate of 20% (N = 225 = 180/0.8), and under plausible assumptions,^{116,117} conservatively provide for 90% compliance increasing for a total of N = 279 ≈ 225/(0.9)(0.9)¹¹⁷ patients.

Table 1: Expected mean CRF Severity scores at 6 weeks post-surgery by age

Group	Age	CRF-Expected	CRF-from R21
IIG	<65	2.5	0.81
IIG	65+	2.0	0.68
WCG	<65	4.5	4.12
WCG	65+	4.2	3.99
ACG	<65	4.3	4.12
ACG	65+	4.0	3.99

Table 2: Power to detect expected differences in mean CRF Severity scores between groups by age

Comparison	Age	Power (N=180)	N for 80% power
IIG vs ACG	<65	0.81	180
IIG vs WCG	<65	0.88	144
IIG vs ACG	65+	0.94	81
IIG vs WCG	65+	>0.99	63

5C) Study Protocol

The following protocol was used successfully in our R21 RCT with the addition of the WCG and ACG in the proposed study. Participants scheduled for NSCLC surgery will be identified by the surgeon's office prior to surgery, recruited, and enrolled by the nurse recruiter.

5C1) Study Interventions.

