5C2) Study Procedures. IIG participants will have baseline data collected by the nurse recruiter. Following principles of transitional care,¹²⁴ the exercise nurse intervener will engage the participant using protocol in Appendix A4 in the hospital post-surgery to review the exercise intervention and teach PSE-enhancing CRF self-management education (Appendix A5) that uses National Comprehensive Cancer Network Guidelines.¹²⁵ To ensure continuity, a primary nurse will be assigned to each participant. Data collectors will contact IIG by phone within approximately 24 hrs of discharge to collect data (if too ill, re-scheduled within approximately 3 days of discharge) and at approximately the end of each week for 6 wks. The nurse will make a phone visit within approximately 24 hrs of post-surgical discharge to screen participant’s readiness to start exercise. Participants will be deemed ready to start if usual level of severity for key symptoms of pain, nausea, and dyspnea are rated ≤ 4 on an 11-point scale (0-10, 10 = most severe). If participant is ready to exercise, a home visit will be scheduled to start exercise within approximately 4 days of discharge. When severity of a key symptom is rated > 4 , nurse will intervene and contact participant’s surgeon’s office for recommendations. The nurse will repeat this step each day until participant is ready to start exercising. Once participant is ready, nurse will arrange home visit within approximately 3 days. The initial home visit will include connecting Wii to participant’s TV, setting up Wii FitPlus log on password, teaching exercise intervention, and reinforcing CRF self-management education and exercise safety precautions. The nurse will follow-up with phone visit within approximately 24 hrs to answer questions and concerns, make a follow-up home visit at approximately the start of wk 2 of exercise, phone visits at approximately the start of wks 3-6, and additional visits per participant request. During visits, nurse will review IIG participant’s Daily Diary (Appendix A2) with participant and provide PSE-enhancing CRF self-management interventions (Appendix A6). These PSE-enhancing interventions include providing mastery and/or vicarious experiences; social encouragement; and reinterpretation of physical and psychological symptoms to support exercise program to adjust exercise prescription per guidelines. Participant uses Daily Diary to record weekly exercise activity and exercise-related symptoms or issues. IIG participants will be given the option to extend exercise for another 6 wks to study wk 12. Data collection will continue on a weekly basis, culminating with a 6MWT at end of approximately wk 12. Nurse calls will continue weekly to prescribe balance exercises and advance walking prescription 5 mins each week, with goal of achieving minimum 30 min/day. Participants may extend beyond 30 min/day with rate of increase no more than 5 min/day each wk, with participants’ PSE for attaining that duration $\geq 70\%$ on a 0-100% scale (100%=high PSE) (Appendix A1).

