
5C2a) WCG participants will have baseline data collected pre-surgery by the nurse recruiter and receive a pedometer and instructions for recording total steps/day in Daily Diary (Appendix A7). The WCG nurse intervener (nurse) will visit in the hospital post-surgery to review study trajectory. Research staff will contact WCG by phone within approximately 24 hrs of discharge to collect post-surgery data (if too ill, data collection rescheduled within 3 days of discharge). Research staff will perform phone visits using protocol in Appendix A8 at the approximate end of wks 1-6 to control for staff interaction and data collection. During wk 6, an exercise nurse intervener will make a phone visit to screen participant’s readiness to start intervention as described for IIG participants. Once participant is ready to start, nurse will arrange home visit within approximately 3 days. The exercise intervention and procedures will be identical to those received by the IIG group during wks 1-6. Staff contact WCG by phone (if too ill, data collection re-scheduled within approximately 3 days) to collect data at the end of approximately wks 7-12.

5C2b) ACG participants will have baseline data collected pre-surgery by a nurse recruiter and receive a pedometer and instructions for recording total steps/day in Daily Diary (Appendix A7). The ACG nurse intervener will visit in the hospital post-surgery to review study trajectory, make a phone visit within approximately 4 days of post-surgical discharge to initiate the ACG intervention (Appendix A3), and make phone visits at the start of approximately wks 2-6. During visits, the nurse will deliver the ACG intervention. Data collectors will contact ACG by phone within approximately 24 hrs of hospital discharge (if too ill, re-scheduled within approximately 3 days of discharge) and at the approximate end of each week for 6 wks to

obtain outcome measures.

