
Section 6.0 Measurement of Effect

As earlier stated following our Specific Aims and Hypothesis, based on existing evidence,⁷²⁻⁷⁵ results of our single-arm pilot (no control group)^{76,77} and two-arm R21 RCT,²³ we expect the benefits of this study to confirm that post-surgical NSCLC patients will find the exercise intervention effective in reducing CRF severity and fatigability (functional capacity). Further, we expect the exercise intervention group will outperform the attention control and wait-list control groups by age for other symptoms' severity; PSE for CRF self-management; PSE for walking; PSE for balance; functional performance; and QOL. We expect the wait-list exercise intervention group's CRF severity and fatigability to improve, but not as significantly as the immediate exercise intervention group. We also expect >50% of the immediate exercise intervention group to extend 6 more wks, with adherence and retention rates of >70% at wk 12, with improved primary and secondary outcomes at wk 12.

Section 7.0 Study Parameters

Measures for Aims 1-3. Aim 1 - Measurement IIG v. ACG and IIG v. WCG Comparisons. Table 3 depicts main study variables and corresponding measures embedded in the concepts of the theoretical framework in Fig 1 (see measures Appendix B1-B9). All measures are administered to all participants using the schedule in Table 3. Participant characteristics as depicted in Table 3 describe the sample. Age is a key biological variable. Given that lung cancer and CRF are significant problems for persons of all ages, and an exercise intervention must be applicable to patients of all ages, study variables will be analyzed for participants by age (< 65 and \geq 65). Also, this study includes men and women as lung cancer is the second most common diagnosed solid tumor with CRF a common symptom for both.¹²⁸ All primary and secondary outcome measures have well established psychometrics, both validity and reliability, with internal consistency scores reported in Table 3 for the cancer

population including use in post-surgical NSCLC.²³⁻²⁴ All measures were used successfully in the R21 RCT without participant complaint about burden. The Karnofsky Performance Scale provides functional impairment classification, universally used in oncology, and is scored from 0% (dead) to 100% (no complaints).¹²⁹

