AEs will be collected from the time the subject signs the consent form until 30 days after the final protocol specified intervention. All AEs will be followed until resolution or a cause is identified. AEs judged by the investigator as not related or probably not related to the treatment will NOT be followed beyond the end of the study.

Section 10.0 Statistical Considerations

Statistical Analysis. All tests of hypotheses will be two-tailed at $\alpha=0.05$. We compare groups at baseline using parametric and non-parametric tests to assess equivalence of confounding physiological and contextual patient characteristics, and pre-surgical outcome variables. If substantive differences exist, they will be controlled for in subsequent analyses by regression techniques, guided by the degree of dissimilarity rather than strict statistical significance.¹⁴⁴

Primary analysis (Aim 1) is the comparison among study groups of the primary outcome CRF severity and fatigability assessed at approximately 6 wks post-surgery. Analysis is based on a regression model for both CRF scores with the following variables in the regression equation: baseline CRF, study group, age, and (if appropriate) plausible interaction between these variables. We test association of study group with outcomes.

In Aim 2 our hypothesis comparing outcomes in IIG and WCG by age group will be addressed in the context of a longitudinal analysis. There are 6 time-ordered differences between IIG and WCG. We use generalized linear (mixed) models to allow flexible correlation structures in the repeated measures.^{145,146} Our regression equation has in addition to the aforementioned variables: time (week) of assessment, and critically, study group with time interactions. The model allows us to test if group effects are changing over time – referred to as a “parallel” profile analysis.¹⁴⁷ If the hypothesis is supported, we test whether that average profiles (over time) in

the two groups are the same. Aim 3 concerns three binary responses in the IIG group at 6 wks: extension, retention, and adherence. Logistic regression models will be used to assess the influence of explanatory variables on the likelihood of outcome.¹⁴⁷⁻¹⁴⁹

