Secondary Outcomes: An analogous strategy is applicable to continuous outcomes assessed at 12 wks. We will use linear models with the caveat that models are conditional on electing to extend participation. Statistical analysis will include intent-to-treat (ITT) analysis and per protocol analysis.^{150,151} ITT principle calls for making inference on the whole sample, with patients as randomized to their study group.¹⁵² To address missingness in our response data we will explore strategies for imputation.¹⁵³ The techniques described above allow missing at random (MAR). Inverse-probability weighting¹⁵⁴ will be investigated to accommodate missing data patterns that are not MAR. Assurance of analysis robustness and minimization of bias: We use a range of outcome measures based on the patient-centered principle to ensure the relevance of the study both biologically and practically. To enhance reproducibility, we will ensure protocol fidelity and follow our analytic plans, including addressing missing data in outcomes. To minimize analysis bias, we will adjust for factors such as potential between group unbalance and examine the robustness of our conclusions under deviations of model assumptions.

Note: Determination of Sample Size is discussed under the Research Design (Section 5, specifically, Section 5B)

TIMELINE. The research timeline is shown in Table 4.

POTENTIAL PROBLEMS AND ALTERNATIVE STRATEGIES. We acknowledge that NSCLC patients after surgery may be subject to complications requiring a break from the intervention. Should participants report unmanaged symptoms or clinical problems, they will be referred to their health care provider per protocol. Should the participant become ill, causing them to miss three consecutive exercise interventions, the participant will be instructed to call their nurse, who will reevaluate and adjust the exercise prescription per protocol. Should the primary nurse intervener become ill or unable to meet with participant, a pre-assigned secondary nurse intervener will step in. There could be diffusion of treatment effects between IIG, WCG, and ACG as well as confounding effects if a disproportionate number of physically active participants are assigned to the IIG, WCG, or ACG. We will assess functional capacity levels and use block randomization to minimize these effects.

Table 4. Research Timeline	Year 1				Year 2				Year 3				Year 4				Year 5			
Activities	Q1	Q2	Q3	Q4																

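### The Aim 1 primary fatigue model uses only the week-6 score, and nothing commits it to the weekly BFI scores that would make its missing-at-random claim credible

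*Combined protocol and SAP*

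**What the plan says.** Section 10.0 defines the Aim 1 primary analysis as the "comparison among study groups of the primary outcome CRF severity and fatigability assessed at approximately 6 wks post-surgery". The model is given next: "Analysis is based on a regression model for both CRF scores with the following variables in the regression equation: baseline CRF, study group, age", with interactions among these where appropriate. It has no time term and no intermediate scores.

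The repeated-measures model comes in the next paragraph, for Aim 2: "We use generalized linear (mixed) models to allow flexible correlation structures in the repeated measures". According to Sections 5A and 7.0, that aim compares weeks 1-6 of the immediate group (IIG) with weeks 7-12 of the wait-list group (WCG). No planned analysis names the week 1-5 scores of the attention control group (ACG).

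The weekly scores will exist. Section 7.0 says "All measures are administered to all participants using the schedule in Table 3", and Table 3 lists the BFI before and after surgery and at weeks 1-12. Section 5C2 has IIG contacted after discharge "and at approximately the end of each week for 6 wks". For WCG, Section 5C2a says "Research staff will perform phone visits using protocol in Appendix A8 at the approximate end of wks 1-6". Section 5C2b sets the same weekly schedule for ACG.

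On losses, Section 5B says "we will over-recruit to account for a conservative attrition rate of 20" per cent. Section 10.0 states the intention-to-treat principle, says imputation strategies will be explored, and adds "The techniques described above allow missing at random (MAR"). It says inverse-probability weighting will be investigated for data that are not MAR. It does not say which of these applies to the Aim 1 primary analysis, which variables would be used, or whether the result would be primary or a sensitivity analysis.

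**The concern.** A participant who leaves after week 4 has four weekly BFI scores, but the Aim 1 regression as written uses none of them. Among completers it estimates the group effect without bias only if the chance of reaching week 6 depends on nothing beyond baseline fatigue, group and age. If a rising week-4 score predicts leaving, the data are MAR given the weekly scores but not given the variables in this model. The general MAR statement is therefore too broad for Aim 1.

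Dropout related to fatigue is plausible from the protocol's own text. Section 2K names fatigue as a barrier for these patients, Section 9.0 cites a review in which people with cancer-related fatigue did not adhere to exercise, and only IIG carries a five-day exercise load in weeks 1-6. At stake is the size of the primary estimate and, if the true effect is small, the type I error.

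**Working it through.** **Inputs from the plan.** Model error SD 2.0; 60 completers per arm (20 aged under 65, 40 aged 65 and over); two-sided alpha 0.05; attrition 20% (Sections 5B and 10.0). Table 1 gives expected differences of 4.3 − 2.5 = 1.8 and 4.0 − 2.0 = 2.0 (IIG vs ACG), and 4.5 − 2.5 = 2.0 and 4.2 − 2.0 = 2.2 (IIG vs WCG).

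**The plan's own figures.** For IIG vs ACG under 65, which sets N: SE = 2.0 × √(2/20) = 0.632; 1.8/0.632 − 1.96 = 0.89; power = 0.81, as stated. Attrition: 180/0.8 = 225, as stated, which is 75 per arm with about 15 lost in each.

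**Crude bound.** If the highest 20% of week-6 scores were lost from one arm only, that arm's mean would shift by SD × φ(0.84)/0.8 = 2.0 × 0.280/0.8 = 0.70 points.

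**Simulation, IIG vs ACG.** 75 per arm, residual SD 2.0, about 20% monotone dropout in each arm, random in ACG and driven by the last recorded fatigue score in IIG. Assumed, because the documents do not give them: the correlation between weeks (compound symmetry 0.5 or 0.7, or AR(1) 0.8) and the log-odds of dropout per SD of fatigue (0.7, 1.5 or 3.0). The completer week-6 regression on baseline, group and age is compared with maximum likelihood using the post-surgery and weekly scores. Negative bias favours exercise. With no true difference:

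| Correlation | Log-odds | Bias, week-6 regression | Bias, weekly scores used | Type I error, week-6 | Type I error, weekly |
|---|---|---|---|---|---|
| CS 0.5 | 0.7 | −0.136 | 0.010 | 0.071 | 0.053 |
| CS 0.5 | 1.5 | −0.251 | 0.012 | 0.120 | 0.049 |
| CS 0.5 | 3.0 | −0.334 | 0.013 | 0.179 | 0.051 |
| CS 0.7 | 0.7 | −0.193 | 0.011 | 0.096 | 0.052 |
| CS 0.7 | 1.5 | −0.345 | 0.011 | 0.177 | 0.044 |
| CS 0.7 | 3.0 | −0.444 | 0.012 | 0.249 | 0.047 |
| AR 0.8 | 0.7 | −0.136 | 0.009 | 0.068 | 0.055 |
| AR 0.8 | 1.5 | −0.249 | 0.010 | 0.114 | 0.053 |
| AR 0.8 | 3.0 | −0.325 | 0.012 | 0.155 | 0.045 |

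The analysis of undropped data shows the same residual of about 0.01, so that part is simulation error. With a true difference of 2.0 the week-6 bias is −0.16 to −0.47 and the weekly-score bias stays within 0.02. The pooled test rejects in every setting.

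**Other settings** (adjacent-week correlation 0.7-0.9, baseline correlation 0.4, difference 2.0):

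- Only IIG dropout follows fatigue: week-6 bias −0.115, −0.166 and −0.250 at correlations 0.7, 0.8 and 0.9; with weekly scores −0.003, 0.015 and 0.006. Across further runs of fatigue-driven dropout the size was 0.05-0.33.
- One rule on the absolute fatigue score in all arms (log-odds 0.7 or 1.5): controls are more fatigued and leave more often (26-30% against 10-14%). The bias is 0.07-0.32 points against exercise in one set of runs and 0.05-0.28 in another.
- Random dropout, or a rule relative to each arm's own mean: bias about zero.

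**Precision under random dropout.** With compound symmetry 0.7 and no true difference, SE falls from 0.372 to 0.341, and 1 − (0.341/0.372)² = 16%. The smallest gain in any run was a variance ratio of 0.97, or 3%.

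**Dropout driven by the unrecorded current score, IIG only.** Week-6 bias is −0.16 to −0.51; with weekly scores it is −0.03 to −0.21, so reduced but not removed.

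**The case against.** A reader might infer that the plan has settled on a completer analysis that discards the weekly data. The documents do not support that. Section 10.0 commits to intention-to-treat inference on everyone randomised and mentions imputation and weighting. Imputing week 6 from the weekly scores would largely remove the problem, and the MAR sentence follows directly on the imputation sentence. This stands. What remains is that these methods are only to be explored or investigated, none is assigned to the primary analysis, and none is tied to the weekly scores.

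A reader might also infer that the bias must favour exercise. That needs fatigue-driven dropout in IIG alone, which no passage predicts. Pilot retention was 97% and adherence 93% (Section 2N), and the 20% is called conservative. Outcome calls are made by data collectors, separately from the exercise nurse (Section 5C2), so stopping exercise need not mean losing BFI scores. One absolute-score rule in all arms gives the opposite sign. Nor can one say that a common dropout rule is harmless: that holds only if it acts relative to each arm's own mean.

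Two further limits stand. Randomisation precedes surgery (Section 4.0), while NSCLC confirmation and post-surgical surgeon approval come later (Section 3.0), so anyone lost at that stage has no weekly scores to use. Fatigability, the other primary outcome, is not measured weekly.

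**Conclusion.** The point holds for CRF severity. The Aim 1 model omits weekly scores that the trial collects in every arm, and the plan fixes no missing-data method that would bring them in. With about 20% missing and dropout following the last recorded score, a completer regression is off by roughly 0.05-0.3 BFI points, and by up to about 0.5 under stronger assumptions. Against the smallest planned difference, 0.14/1.8 = 8% and 0.47/1.8 = 26%. The sign is not known in advance, and the bias is about zero if dropout is random. All of this rests on assumed correlations and dropout strengths.

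At the planned differences of 1.8-2.2 points the trial's conclusion would probably not change. That was checked for the pooled contrast only; the under-65 comparison, with 0.81 power, has less margin. The realistic harm is a distorted effect estimate or, if the true effect is small and dropout follows fatigue in one arm only, type I error of about 7-25% instead of 5%. An absolute-score rule common to all arms would not cause false positives, because with no true difference it acts alike in each arm.

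**What to change.** Make the primary CRF-severity analysis a repeated-measures model on BFI weeks 1-6 in all three arms, with group by week, baseline BFI by week, age, group by age by week, and unstructured covariance. Take the week-6 IIG-ACG and IIG-WCG contrasts, overall and by age group, as the primary estimates. The age terms must stay because Section 5B sets N on age-specific comparisons. Multiple imputation of week 6 from the weekly scores, with the same age terms, is an acceptable equivalent; either should be named in the SAP before outcome data are seen.

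Keep the present week-6 regression as a sensitivity analysis, and add one for dropout that depends on unrecorded fatigue, which the repeated-measures model does not cure. For fatigability, use the weekly BFI scores as auxiliary variables in imputation.

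The cost is SAP wording and some programming. No new data or visits are needed, and N does not change.

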Our **long-term goal** is to develop interventions to increase perceived self-efficacy (PSE), perception of ability, for CRF self-management as a means of improving functional status and quality of life for persons with NSCLC.²⁵ Our **objective** in this application is to determine the efficacy, optimal timing of initiation, and sustainability of our 6-wk home-based exercise intervention. The **significance** of this study is that it targets two of the most troublesome unmet needs, fatigue and lack of exercise, in an understudied, vulnerable population with the potential to **transform** the current standard of care by providing a rehabilitative exercise intervention after surgery. The proposed research advances the field by providing both an intervention for CRF self-management and evidence for its optimal initiation and sustainability, which currently does not exist for the post-thoracotomy NSCLC population. Our exercise intervention is guided by a theoretical approach (tested by the PI) incorporating self-efficacy theory to strengthen a person's ability to manage their CRF and walking ability.^{17,26} The exercise intervention is **innovative** in its timing and approach in providing self-paced exercise to a vulnerable post-surgical NSCLC population upon discharge from the hospital. The Nintendo's Wii Fit Plus is used to provide light-intensity, virtual reality walking and balance exercise that departs from the status quo and transcends barriers to exercise, as demonstrated by our R21 RCT retention and adherence outcomes.

This study employs a three-arm RCT for persons undergoing NSCLC surgery with participants being randomly assigned to an immediate (post-hospital discharge) exercise intervention group, a wait-list control group (6 wks usual care [wks 1-6] and 6 wks exercise [wks 7-12]), or a 6 wk attention control group (wks 1-6).

Protocol Version 4.0 (7/19/2023). UNMC IRB 560-18 EP. Contact PI: [name] [name], RN.

Primary Outcome: Cancer-Related Fatigue (Severity and Fatigability).

Secondary Outcomes: Severity of Other Symptoms; PSE for CRF Self-Management, Walking, and Balance; Functional Performance; and Quality of Life (QOL).

Aim 1: Determine efficacy of three groups by comparing: 1) immediate exercise intervention group; 2) a wait-list control group; 3) an attention control group by age. Hypothesis 1: The exercise intervention group will outperform wait-list and attention control on all primary and secondary outcomes at wk 6 for all ages.

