An intervention must be applicable to patients of all ages. Oksholm et al. report few age-related differences among 270 persons undergoing surgery for lung cancer, noting that fatigue and multiple symptoms are highly prevalent in both younger (< 65) and older (> 65) patients.⁵⁴ While fatigue is a major issue among all ages, fatigue is prevalent in older adults (> 65) and interferes with activity, leading to loss of independence.⁵⁵ Among older adults void of mobility limitations or disability, fatigue when performing activities such as walking (fatigability) is predictive of activity limitations, functional decline, and disability.⁵⁶⁻⁵⁹ In persons 75-80 yrs old, sustained fatigue was found to be a strong predictor of mortality.⁶⁰ With 67% of persons diagnosed with lung cancer aged 65+ at time of diagnosis,⁶¹ and fatigue identified as a priority symptom, it is critical to have an intervention that is effective and applicable to lung cancer patients of all ages.^{15,16,20} Results of our R21 RCT indicate the exercise intervention was beneficial for both younger (<65) and older (> 65) patients with CRF severity of both groups improving by a mean of 3.3 (scale 0-10, 10 = most severe) over their corresponding control groups post-intervention.

2C). SIGNIFICANT CONTRIBUTION

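### Section 10 does not carry into the Aim 1 primary analysis the age-specific CRF-severity contrasts on which Section 5B sizes the trial

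*Combined protocol and SAP*

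**What the plan says.** **Sizing.** Section 5B chooses N to give "at least 80% power in 4 pre-specified comparisons". Table 2, titled "Power to detect expected differences in mean CRF Severity scores between groups by age", lists IIG vs ACG and IIG vs WCG, each in <65 and ≥65, with minimum N of 180, 144, 81 and 63. The sentence in 5B, however, describes the four comparisons as being of IIG with ACG only.

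**Intent.** Aim 1 is framed by age. Hypothesis 1 expects IIG to do better than both controls "on all primary and secondary outcomes at wk 6 for all ages". Section 7.0 says that "study variables will be analyzed for participants by age", with the cut at 65.

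**Primary analysis.** Section 10.0 models the week-6 outcome on "baseline CRF, study group, age, and (if appropriate) plausible interaction between these variables". The only Aim 1 test it names is: "We test association of study group with outcomes". On sample size it only points back: "Determination of Sample Size is discussed under the Research Design".

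**Randomisation.** Section 4.0 blocks on age (cut at 65) and on 6MWT distance (452 m or more). The second factor does not appear in the Section 10 model.

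**The concern.** The comparisons that fix the trial's size are not named as tests in the primary analysis. Section 10 does not name group-by-age, does not say when an interaction counts as appropriate, and does not say whether age enters as the <65/≥65 factor. With the term left out, the model gives one difference per pair of arms, averaged over age with weights of one third (<65) and two thirds (≥65). It then has no separate estimate for patients under 65, although a contrast in that age group determines N.

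The stake is the claim for all ages. A significant age-averaged result is compatible with no benefit in the younger third, and whether to look further would be decided after the data are seen.

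**Working it through.** **Inputs.** From Section 5B and Table 1: error SD 2.0; 20 patients <65 and 40 patients ≥65 per arm at N=180. Expected means for <65 / ≥65 are IIG 2.5 / 2.0, WCG 4.5 / 4.2, ACG 4.3 / 4.0. From Section 10.0: two-sided 5%.

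**1. Reproduce Table 2.** The SE of a within-age contrast is 2.0 × √(2/n):
- <65: 2.0 × √(2/20) = 0.632
- ≥65: 2.0 × √(2/40) = 0.447

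Power is from the noncentral t with 172 residual df. The smallest N keeps whole cells at the 1:2 age split, so it moves in steps of 9.

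| Contrast | Difference | Difference/SE | Power | Table 2 power | Smallest N | Table 2 N |
|---|---|---|---|---|---|---|
| IIG–ACG, <65 | 1.8 | 2.85 | 0.808 | 0.81 | 180 | 180 |
| IIG–WCG, <65 | 2.0 | 3.16 | 0.882 | 0.88 | 144 | 144 |
| IIG–ACG, ≥65 | 2.0 | 4.47 | 0.994 | 0.94 | 81 | 81 |
| IIG–WCG, ≥65 | 2.2 | 4.92 | 0.998 | >0.99 | 63 | 63 |

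All four N reproduce, and so do three of the four powers. The printed 0.94 does not, but it errs on the low side, does not affect N, and is not relied on here. Table 2 is therefore built on separate within-age contrasts, each at unadjusted 5%, and the first row alone requires 180.

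**2. What the model gives without the interaction.** The averaged differences are
- IIG–ACG: (1.8 + 2 × 2.0)/3 = 1.93
- IIG–WCG: (2.0 + 2 × 2.2)/3 = 2.13

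The SE is 2.0 × √(2/60) = 0.365. Power at N=180 exceeds 0.999 for both, and 80% power would need N=54 and N=45. For CRF severity this is a much less demanding target than the one in 5B.

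**3. Can the averaged test support a claim for all ages?** Suppose, for illustration, that the IIG–ACG benefit is 2.0 in ≥65 and 0 in <65. The averaged difference is (0 + 2 × 2.0)/3 = 1.33, and 1.33/0.365 = 3.65. Power is Φ(3.65 − 1.96) ≈ 0.95. The averaged test would nearly always be significant with no effect in <65.

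**4. How often would the interaction enter?** The plan gives no rule. If significance decided it (an assumption), then under Table 1 the benefit differs between age groups by 2.0 − 1.8 = 0.2, with SE 2.0 × √(2/20 + 2/40) = 0.775. The ratio is 0.26 and power is about 6%, so the term would usually be left out.

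**5. Precision.** 95% half-widths at N=180, with t = 1.974: 1.974 × 0.632 = 1.25 points (<65), 1.974 × 0.447 = 0.88 (≥65) and 1.974 × 0.365 = 0.72 (averaged). The averaged interval shows a precision that the <65 group does not have.

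**6. Cost of the fuller model.** Group × age group and the 6MWT stratum use a few df. Power for the smallest contrast is 0.808 at 176, 174 or 172 residual df.

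**7. Error level.** If the overall 5% in Section 5B means familywise control over the four contrasts, the smallest contrast has power of about 0.78 with Holm (200,000 simulations under Table 1) and 0.63 with Bonferroni (0.0125 each), against the stated 0.81.

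**The case against.** The strongest reply is that by-age analysis is already promised. Aim 1, Hypothesis 1 and Section 7.0 all say so, Section 5B calls the comparisons pre-specified, and protocol and SAP are one document. Section 10 also permits the interaction. This stands as far as intent goes. A reader might infer that no age-specific result will be produced; the documents do not support that. What is missing is narrower: none of these places names a model term or test, and the section that does so leaves the term to discretion.

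A reader might infer from the N of 54 and 45 that N=180 is justified only if the age contrasts are reported. That goes too far. Those figures are for CRF severity. Fatigability is also a primary outcome, and no power is given for it, so the documents do not show what N it needs.

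A reader might also expect a wrong overall conclusion. The plan's own figures point the other way: in Table 1 the averaged IIG–ACG difference is 1.93 against 1.8 and 2.0 by age, and Section 2B reports the pilot intervention as "beneficial for both younger (<65) and older (> 65) patients".

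On the 6MWT factor, it is fair to say that Section 10 already allows adjustment for substantive baseline imbalance. Leaving out a randomisation factor does not bias the comparison or raise the false-positive rate. It makes standard errors conservative, by an amount the documents do not let us derive.

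**Conclusion.** The concern holds as a specification gap that should be closed before analysis. Section 5B sizes the trial on within-age CRF-severity contrasts, and Section 10, followed literally, can omit them and test only the study-group association. That test cannot support Hypothesis 1 for all ages: it keeps about 95% power when the IIG–ACG benefit is confined to ≥65. Under the Table 1 means, the expected loss is the age-specific result and not the overall conclusion. The missing 6MWT factor is a minor precision point.

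The figures rest on Table 1, SD 2.0, the 20/40 split and unadjusted two-sided 5% per contrast. The 95% figure uses an illustrative effect pattern, and the 6% figure assumes a significance rule that the plan does not state. Taking Table 2 as the list of the four comparisons is a reading, because the 5B sentence mentions ACG only.

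**What to change.** In Section 10.0, replace both the Aim 1 model sentence and the test sentence with:

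> The week-6 value will be regressed on its own baseline value, study group, age group (<65, ≥65), study group × age group (always included) and 6MWT stratum (≥452 m or not). For CRF severity, the four comparisons of Table 2 will be estimated and tested from this model with 95% confidence intervals. The same contrasts will be reported for fatigability, for which no power is stated.

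Replacing the model sentence alone would leave the study-group association as the only named test. Other interactions, if wanted, can be kept as sensitivity analyses.

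In Section 5B, reconcile the sentence that describes the four comparisons as IIG with ACG with Table 2, which also lists IIG vs WCG.

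**Cost.** Wording and a few degrees of freedom. All the variables are already collected. N=180 and power of 0.81 for the smallest contrast stand at unadjusted two-sided 5%. State what the overall 5% in Section 5B means; if it is familywise control, restate the power (about 0.78 with Holm or 0.63 with Bonferroni for the smallest contrast).
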